Total bilirubin	$\leq 1.5 \times$ ULN OR $< 3.0 \times$ ULN for patients who have Gilbert's syndrome
ALT and AST	$\leq 2.5 \times$ ULN OR $\leq 5 \times$ ULN if the liver has tumor involvement
Renal	
Serum creatinine OR Calculated creatinine clearance (see Appendix 6)	$\leq 1.5 \times$ ULN OR ≥ 50 mL/min

Abbreviations: ALT = alanine aminotransferase; ANC = absolute neutrophil count; aPTT= activated partial thromboplastin time; AST = aspartate aminotransferase; ULN = upper limit of normal

- [10] Have a performance status of 0 or 1 on the Eastern Cooperative Oncology Group scale (Oken et al. 1982).
- [11] Have discontinued previous treatments for cancer and recovered from the acute effects of therapy. Patients must have discontinued from previous treatments, as shown in the table below:

Previous Treatment	Length of Time Prior to First Dose of Study Treatment
Cytotoxic therapies or targeted agents (small molecule inhibitors)	≥14 days
Mitomycin-C or nitrosoureas	>42 days
Biologic agents (including immunotherapy)	≥21 days
Radiotherapy	≥28 days
Limited field radiotherapy for palliative intent	≥14 days
Major surgery, excluding biopsy	Patients with major surgery within 28 days prior to starting therapy must have recovered in the opinion of the investigator.

- [12] Are reliable and willing to make themselves available for the duration of the study and are willing to follow study procedures.
- [13] Men with partners of childbearing potential or women with childbearing potential must agree to use a highly effective contraceptive method of birth control (Appendix 1) during study treatment and for at least 6 months following the last dose of study drug.
- [14] Women of childbearing potential must have a negative serum pregnancy test documented within 7 days prior to initiation of treatment.
- [15] Have an estimated life expectancy ≥12 weeks, in the judgement of the investigator.

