Cardiac	Myocarditis, cardiac function abnormalities (for example, dysrhythmia, valvular abnormalities)	≥1		
 Discontinue study treatment and administer 
 IV methylprednisolone 2-4 mg/kg/day Consider immunosuppressives without immediate response to steroids (for example, mycophenolate, infliximab, or anti-thymocyte globulin) Consult with cardiology immediately and Lilly CRP/CRS; if available, transfer to cardiac care unit
Renal and urinary	Elevated creatinine, decreased urine output, blood in urine, edema, nephritis	1	<1.5 x baseline	Continue study treatment
		2-3	1.5 × ULN < × ≤ 6 × ULN or >1.5 × baseline	
 Withhold study treatment and administer prednisone 0.5-1 mg/kg/day Resume study treatment after the event resolves to Grade ≤1 If elevations persist for >7 days or worsen, follow the guidelines for a Grade 4 event
		4	>6 × ULN	Discontinue study treatment and administer prednisone 1-2 mg/kg/day

Dose Modification Guidelines and AE Management for Toxicities At Least Possibly Related to Study Drug

SOC	Toxicity	CTCAE Grade and/or Symptoms ^a		Treatment Plan ^b
		Grade	Symptoms	
Skin	Rash, pruritus		Moderate rash (diffuse, ≤30% BSA)	
 Withhold study treatment For rash on <10% of the patient's BSA, administer intermediate or high-potency topical corticosteroid For rash on 10%-30% of the patient's BSA, administer systemic corticosteroids Resume study treatment if the rash improves to mild (localized) and the corticosteroid dose is <7.5 mg/day
	Stevens–Johnson syndrome, toxic epidermal necrolysis, necrosis, bullous or hemorrhagic lesions			Discontinue study treatment and administer prednisone 1-2 mg/kg/day
Ophthalmological	Eye disorders (for example, uveitis, episcleritis)	≥2		
 If mild, consider topical steroids (for example, 1% prednisolone); otherwise, discontinue study treatment and administer 
 Oral or IV methylprednisolone 2-4 mg/kg/day Consult ophthalmologist and Lilly CRP/CRS.

Dose Modification Guidelines and AE Management for Toxicities At Least Possibly Related to Study Drug

Abbreviations: ADL = activities of daily living; ALT = alanine aminotransferase; AST = aspartate aminotransferase; BSA = body surface area; CRP = clinical research physician; CRS = Clinical Research Scientist;

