CTCAE = Common Terminology Criteria for Adverse Events, Version 4.0; irAE = immune-related adverse event; IV = intravenous; SOC = system organ class; TB = total bilirubin; ULN = upper limit of normal.

- a If symptoms of grade is not specified, use CTCAE Version 4 definitions; otherwise, use the definitions provided in this table.
- b Discontinuation of study treatment is permanent; resumption of study treatment is not allowed. If a toxicity does not resolve to Grade 0-1 or if the corticosteroid dose cannot be reduced to ≤ 10 mg/day of prednisone or equivalent within 12 weeks, consult with the Lilly CRP/CRS about discontinuing study treatment.
- c Immunosuppressive refers to infliximab or cyclophosphamide.
- d Patients who have asymptomatic or clinically non-significant Grade 3 or 4 lipase or amylase elevations (for example, not associated with clinical symptoms or radiological signs of pancreatitis) that are transient as demonstrated by a decrease of at least 1 CTCAE Grade within 7 days (± 3 days) of onset will not require discontinuation of LY3415244. If the elevation does not decrease by at least 1 CTCAE Grade within this time window, LY3415244 treatment may continue only after consultation and discussion with the Lilly CRP/CRS.

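### The renal rows of Table JZDA.7.4 contradict each other when baseline creatinine is above 1.0 × ULN: one value can call for both continuing and withholding treatment

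*Protocol*

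**What the plan says.** The Renal and urinary block of Protocol Table JZDA.7.4 has three rows.

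- **Grade 1:** creatinine "<1.5 x baseline". Study treatment continues.
- **Grade 2-3:** "1.5 × ULN < × ≤ 6 × ULN or >1.5 × baseline". Treatment is withheld, prednisone is given, and treatment resumes once the event is back to Grade 1 or lower. The row adds: "If elevations persist for >7 days or worsen, follow the guidelines for a Grade 4 event".
- **Grade 4:** above 6 × ULN. "Discontinue study treatment and administer prednisone 1-2 mg/kg/day".

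Footnote a uses CTCAE Version 4 where the table gives no grade or symptom definition; "otherwise, use the definitions provided in this table". Footnote b states: "Discontinuation of study treatment is permanent; resumption of study treatment is not allowed".

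Inclusion criterion [9] (Section 6.1) accepts serum creatinine up to 1.5 × ULN or, as an alternative, a calculated clearance of at least 50 mL/min by the Appendix 6 formula.

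**The concern.** The rows are graded against different references. Grade 1 looks only at the ratio to baseline and has no ULN limit. Grade 2-3 can be met through the ULN alone, whatever the baseline. A patient who starts with creatinine above normal can therefore satisfy both rows with one result.

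The two instructions are opposite, and one branch cannot be reversed: withholding turns into a permanent stop if the elevation persists for more than 7 days or worsens. Short of a stop, the withhold row brings a course of prednisone, and Section 7.4 bars restart until a one-month corticosteroid taper is complete. The condition for resuming has the same defect, because a value in the overlap is both Grade 1 and Grade 2-3.

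Two sites could follow the table faithfully and act differently on the same result. The difference would show in the SAP summaries of dose adjustments and their reasons (Section 5.12.1) and of adverse events as the reason for stopping treatment (Section 5.12.3). It would also enter the RP2D discussion, which names dose adjustments as an input (Protocol Section 7.2.2.3).

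**Working it through.** The plan states no figure here to reproduce. The check applies the printed thresholds to a baseline *b* and an on-study value *v*, both in multiples of ULN. The middle symbol in the Grade 2-3 range is read as the creatinine value.

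**Step 1. Write the rows as conditions.**

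- Grade 1 (continue): v < 1.5b
- Grade 2-3 (withhold): 1.5 < v ≤ 6, or v > 1.5b
- Grade 4 (discontinue): v > 6

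**Step 2. Find the overlap of Grade 1 and Grade 2-3.** Both hold when 1.5 < v < 1.5b, with v no higher than 6. This range is non-empty exactly when b > 1.0.

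| Baseline b (× ULN) | Values meeting both rows (× ULN) | Rise from baseline that reaches 1.5 × ULN, 1.5/b − 1 |
|---|---|---|
| 1.0 | none | 50% |
| 1.1 | 1.50 to 1.65 | 36% |
| 1.2 | 1.50 to 1.80 | 25% |
| 1.3 | 1.50 to 1.95 | 15% |
| 1.4 | 1.50 to 2.10 | 7% |
| 1.5 | 1.50 to 2.25 | 0% |

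Worked case: b = 1.3 and v = 1.6. The ratio is 1.6/1.3 = 1.23, below 1.5, so Grade 1 applies. Also 1.6 > 1.5, so Grade 2-3 applies.

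**Step 3. Check that such patients can be enrolled.** Baselines from 1.0 to 1.5 × ULN are eligible on creatinine alone. Higher baselines can be eligible through clearance. Appendix 6 gives, for men, CrCl = (140 − age) × weight / (72 × creatinine in mg/dL). The ULN in mg/dL is not in the documents, so 1.0, 1.2 and 1.3 are assumed.

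- Age 40, 100 kg, creatinine 2.05 mg/dL: 100 × 100 / (72 × 2.05) = 67.8 mL/min, eligible. This is 2.05, 1.71 or 1.58 × ULN, above 1.5 under all three assumptions.
- Age 55, 80 kg, at the 50 mL/min limit: creatinine = 85 × 80 / (72 × 50) = 1.89 mg/dL. This is 1.89, 1.57 or 1.45 × ULN, so here the answer depends on the ULN.

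With b = 1.6 and no change at all (v = 1.6), the ratio to baseline is 1.0 and v exceeds 1.5. Both rows are met, and a return to baseline does not settle whether the event has resolved to Grade 1.

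**Step 4. Look for a tie-breaker.** Footnote a directs the reader to the table's own definitions where they exist, so CTCAE grading does not decide. No text says that the higher row governs.

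**Step 5. Two smaller gaps in the same rows.** A value of exactly 1.5 × baseline that is not above 1.5 × ULN falls in no row. The baseline limb of Grade 2-3 has no upper limit, so it also overlaps Grade 4: at b = 1.0 and v = 6.5 both apply.

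**The case against.** The best case for leaving the table alone is that it is guidance filtered by judgment. It covers only events considered at least possibly related to study drug. Section 7.4 calls for a workup of other causes and encourages consultation with the sponsor. A value moving around an already raised baseline is the kind of finding that this judgment can screen out. Section 7.4 also lets local-standard guidelines supersede the table where the investigator thinks fit, so some variation between sites is accepted by design and rewording one block would not remove it. In Phase 1a, no dose modification is allowed in Cycle 1.

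All of this stands as a limit on how often the contradiction will matter. None of it resolves the contradiction: an investigator who judges a rise possibly related and turns to the table still finds two answers.

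A reader might also infer that renal holds and stops would often be produced by ordinary fluctuation in creatinine. The documents do not support that. They give neither the within-patient variability nor the distribution of baseline creatinine. The chance of crossing 1.5 × ULN is not the chance of a hold, because relatedness is judged first, and still less of a stop, which needs persistence beyond 7 days or worsening. No rate is claimed here.

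**Conclusion.** The renal rows are wrong as written: for baseline creatinine above 1.0 × ULN they give opposite instructions over a definable range, and one of those instructions can end in permanent discontinuation. This follows from the printed thresholds and criterion [9] alone. Only the examples with baseline above 1.5 × ULN need an assumed laboratory ULN.

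The weight is minor to moderate. The number of patients affected cannot be derived from the documents, and patients with baseline at or below 1.0 × ULN do not meet the overlap between Grade 1 and Grade 2-3. The outputs touched are the dose-adjustment and discontinuation summaries and the RP2D discussion.

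A reader might infer that the primary safety results as a whole are compromised. That goes too far. DLTs are judged against Table JZDA.7.2, and SAP Section 5.12.5 calculates laboratory grades from CTCAE; neither uses these rows. SAP Section 5.6 plans no formal hypothesis testing, so no powered comparison is affected.

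**What to change.** Reconcile the three renal rows with each other and with inclusion criterion [9], so that every creatinine value maps to one instruction, including for patients who enter above 1.5 × ULN through the clearance alternative. State which reference, ULN or baseline, is used to judge persistence beyond 7 days, worsening, and resolution to Grade 1 or lower. Close the two smaller gaps (exactly 1.5 × baseline, and the overlap with Grade 4) in the same edit. Which rule to adopt is a clinical decision for the sponsor, and none is proposed here.

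The cost is a wording change to one block of one table at the next amendment. No new tests, visits or data are needed.

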7.5. Preparation/Handling/Storage/Accountability

LY3415244 should be stored under refrigerated conditions (2°C to 8°C).

7.6. Treatment Compliance

The study medication will be administered only at the investigational site by the authorized study site personnel. As a result, treatment compliance is ensured.

7.6.1. *Evaluable Patients*

7.6.1.1. DLT-Evaluable Patients in Phase 1a

A patient will be DLT evaluable if he or she experiences a DLT during the DLT observation period and has received at least 1 dose of study drug.

If a patient does not experience a DLT during the DLT observation period, he or she will be DLT evaluable if he or she receives all assigned doses of study drug(s) during the DLT observation period

Patients who receive all doses of study drug but discontinue from study treatment before the end of the DLT observation period will be considered DLT evaluable for the assessment of a dose level, provided it can be documented that the patient did or did not experience a DLT within the DLT observation period.

Patients who are not DLT evaluable may be replaced to ensure that enough patients complete the DLT observation period at each dose level, unless accrual to that cohort has stopped due to a DLT.

A patient may be deemed non-evaluable for assessment of a dose level in the event the patient experiences an AE which would meet DLT criteria, and furthermore has been determined through discussion between investigator and Lilly CRP/CRS to most likely be related to a

concomitant medication or a prior line of immune therapy (in the case of irAEs) due to previously established linkage. Adverse events from DLT non-evaluable patients will also be reviewed throughout the dose escalation process in Phase 1a.

To ensure collection of adequate PK or biomarker data, patients who complete the DLT observation period but who do not have a valid PK or biomarker assay result may be replaced, upon consultation with the investigator(s) and the Lilly CRP/CRS, unless accrual to that cohort has stopped because of a DLT. Patients who are replaced for purposes of the PK or biomarker analysis are still considered DLT evaluable.

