	
Stop the infusion and proceed with following:
 
 1. If resolved to Grade 0 or 1 within 1 hour after stopping the infusion 
 a. restart the infusion at 50% of the original rate (for example, reduce from 100 to 50 mL/hr) 2. If NOT resolved to Grade 0 or 1 within 1 hour after stopping the infusion: 
 a. delay study treatment until the symptoms resolve in \leq48 hours, and b. premedicate prior to the next scheduled dose. Premedication should be administered 1.5 hours (\pm30 minutes) prior to the LY3415244 infusion with diphenhydramine (or other antihistamine), acetaminophen (or other antipyretic), steroids etc., at the discretion of treating physician.
3 or 4	
Second occurrence
 
Immediately and permanently discontinue study treatment
 
Immediately and permanently discontinue study treatment.
 
Patients who experience a Grade 3 IRR that resolves within 6 hours may continue on study treatment. For subsequent infusions, the patient should be premedicated 1.5 hours (\pm30 minutes) prior to the LY3415244 infusion with diphenhydramine (or other antihistamine), acetaminophen (or other antipyretic), steroids etc., at the discretion of treating physician.
 
If symptoms reappear, immediately and permanently discontinue study treatment.

Table JZDA.7.4 presents guidance for irAE management (including use of corticosteroids) and criteria for dose delays and discontinuations if the patient experiences a potential irAE considered at least possibly related to LY3415244.

Because of the potential for rapid and serious sequelae associated with irAEs, early intervention with corticosteroids is encouraged, concurrent with further diagnostic medical evaluations for possible nonimmune-related causes of AEs. The treatment plan should always include a thorough workup of the issue to rule out other potential etiologies such as infection. Guidelines used by local standards such as, but not limited to Haanen and colleagues (2017), Puzanov and colleagues (2017), or Brahmer and colleagues (2018), supersede the guidelines provided in Table JZDA.7.4 if deemed appropriate by the investigator. If a patient experiences an irAE that is not listed in this table, consult the Lilly CRP/CRS to discuss appropriate management.

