10.2. Populations for Analyses

The following analysis sets will be defined for this study:

Enrolled/Safety population: will include all patients who received any quantity of study treatment, regardless of their eligibility for the study. The safety and efficacy evaluation will be performed based on the first dose of study treatment a patient actually received. This population will be used for all dosing/exposure, safety, and efficacy analyses.

Pharmacokinetic population: will include all enrolled patients from whom a valid assay result (according to laboratory guideline) has been obtained.

Biomarker population: will include the subset of enrolled patients from whom a valid assay result has been obtained. No imputation will be performed for missing data due to the limitation of small sample size.

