Appendix 1. Abbreviations and Definitions

Term	Definition
ADA	anti-drug antibody
AE	Adverse event: any untoward medical occurrence in a patient or clinical investigation patient administered a pharmaceutical product and does not necessarily have a causal relationship with this treatment. An adverse event can therefore be any unfavorable and unintended sign (including an abnormal laboratory finding), symptom, or disease temporally associated with the use of medicinal (investigational) product, whether or not related to the medicinal (investigational) product.
ALT	alanine aminotransferase
ASCO	American Society of Clinical Oncology
AST	aspartate aminotransferase
AUC	area under the concentration-time curve
AUC_{0-2wk}	area under the concentration versus time profiles of a 2-week dosing interval
BOR	best overall response
C_{avg}	2-week average concentration
C_{max}	maximum plasma concentration
C_{min}	trough concentration
CI	confidence interval
CNS	central nervous system
collection database	A computer database where clinical study data are entered and validated.
CR	complete response
CrCl	creatinine clearance
CRP	clinical research physician: individual responsible for the medical conduct of the study. Responsibilities of the CRP may be performed by a physician, clinical research scientist, global safety physician or other medical officer.
CRS	clinical research scientist
CSR	clinical study report

CT	computed tomography
CTCAE	Common Terminology Criteria for Adverse Events
CTLA-4	cytotoxic T-lymphocyte-associated protein 4
C_{trough}	lowest concentration of drug just prior to the next dose
DCR	disease control rate: the percentage of patients with a best response of CR, PR, or SD.
DLT	dose-limiting toxicity
DoR	duration of response: the time from the date measurement criteria for CR or PR (whichever is first recorded) are first met until the first date that disease is recurrent or objective progression is observed, per RECIST 1.1 criteria, or the date of death from any cause in the absence of objectively determined disease progression or recurrence.
ECG	electrocardiogram
eCRF	electronic case report form
EGFR	epidermal growth factor receptor
EI	equivalence interval
enroll	The act of assigning a patient to a treatment. Patients who are enrolled in the study are those who have been assigned to a treatment and have received at least one dose of study treatment.
ERBs/IRBs	ethical review boards/institutional review boards
ELISA	enzyme-linked immunosorbent assay

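### A patient whose Cycle 1 infusion was cut short can be counted as a full DLT-free patient, because the protocol leaves an interrupted infusion undefined and SAP 5.2.1 drops the dose condition

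*Protocol*

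**What the plan says.** **Evaluability in the protocol.** Section 7.6.1.1 has one clause for patients with a DLT and one for those without. A patient is evaluable who "experiences a DLT during the DLT observation period and has received at least 1 dose of study drug". If there was no DLT, "he or she will be DLT evaluable if he or she receives all assigned doses of study drug(s) during the DLT observation period". A third sentence covers patients who stop treatment before the end of Cycle 1; it too applies only to those who had all their doses. "Patients who are not DLT evaluable may be replaced", subject to accrual still being open. No minimum amount of an infusion is set.

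**Evaluability in the SAP.** Section 5.2.1 has two routes into the DLT-evaluable population: finishing the Cycle 1 observation period, or stopping treatment earlier with a DLT assessment on record. Neither route mentions doses. SAP 5.12.2 summarises DLTs on this population.

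**Interrupted infusions.** Table JZDA.7.3 (Protocol 7.4) stops the infusion at a first Grade 2 reaction. If the reaction settles within an hour, the infusion restarts at half rate. The other branch ("If NOT resolved to Grade 0 or 1 within 1 hour after stopping the infusion") delays treatment and calls for premedication before the following dose; what happens to the undelivered remainder is not addressed. For more severe reactions the table ends treatment, with an exception: "Patients who experience a Grade 3 IRR that resolves within 6 hours may continue on study treatment". Section 7.2.2.2.1 exempts a first Grade 3 infusion reaction from being a DLT if no corticosteroid prophylaxis was given and it resolves within 6 hours.

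**The concern.** Read together, these sections foresee a patient who was partly infused, had no DLT by definition and remains on study. Protocol 7.6.1.1 does not settle whether that patient counts. SAP 5.2.1, as written, counts the patient.

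The number of patients is the denominator of each mTPI-2 decision, and Appendix 7 labels its columns simply by patients dosed. A patient who received only part of the assigned amount says less about toxicity at that dose level than a fully dosed one. Counting that patient as one more DLT-free observation lowers the apparent DLT rate, and cohorts may be as small as three. The error runs in one direction, towards a higher dose.

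**Working it through.** **Inputs.** Target DLT rate 30%, equivalence interval 25% to 35%, minimum 3 patients per cohort (Protocol 7.2.2.1); maximum 10 per dose level (5.2); two infusions in Cycle 1, on Days 1 and 15 (Table JZDA.7.1); decision grid in Appendix 7. The documents give no rate of interrupted infusions.

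**Step 1: reproduce the plan's decisions.** I assumed a Beta(1,1) prior, intervals of width 0.10 built out from (0.25, 0.35), and DU when the posterior probability that the rate exceeds 0.30 is above 0.95. This gives 1/3 Stay, 1/6 Escalate, 2/3 De-escalate and 5/7 DU, as in the Appendix 7 examples, and 2/6 Stay, as in Section 7.2.2.1. All five agree. The comparisons below use only cells with one or two DLTs.

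**Step 2: who counts under each document.**

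| Phase 1a patient | Protocol 7.6.1.1 | SAP 5.2.1 |
|---|---|---|
| No DLT, both infusions complete, Cycle 1 completed | Evaluable | Evaluable |
| No DLT, one infusion stopped and not completed, Cycle 1 completed | Not settled: depends on whether a part-infusion is a dose | Evaluable |
| No DLT, Day 1 infusion only, then stopped, DLT status documented | Not evaluable | Evaluable |
| DLT during the first infusion, then stopped | Evaluable on the natural reading (see objection) | Evaluable |

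The third row is a direct conflict whatever *dose* means. The second is the gap that both documents share.

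**Step 3: effect on the grid.** Compare *x* DLTs in *n* − 1 patients (partly infused patient left out) with *x* in *n* (counted).

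| Left out | Counted |
|---|---|
| 1/2 De-escalate | 1/3 Stay |
| 1/4 Stay | 1/5 Escalate |
| 2/5 De-escalate | 2/6 Stay |
| 2/8 Stay | 2/9 Escalate |

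Each change is towards a higher dose. Many cells do not change; 1/5 and 1/6, for example, are both Escalate.

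**Step 4: bound on the chance of escalating.** With three patients, escalation needs 0/3. Let *p* be the true DLT rate and let the partly infused patient carry a fraction *k* of that risk:

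P(0/3) = (1 − p)² × (1 − k·p)

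| | k = 1 (no loss) | k = 0.5 | k = 0 (worst case) |
|---|---|---|---|
| p = 0.30 | 0.7³ = 0.343 | 0.49 × 0.85 = 0.4165 | 0.7² = 0.490 |
| p = 0.50 | 0.5³ = 0.125 | 0.25 × 0.75 = 0.1875 | 0.5² = 0.250 |

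With six patients, escalation needs 0 or 1 DLT. At p = 0.30 the chance is 0.7⁶ + 6 × 0.3 × 0.7⁵ = 0.420 with all six fully dosed. It is 0.7⁵ + 5 × 0.3 × 0.7⁴ = 0.528 if one of them carries no risk.

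These figures are conditional on exactly one such patient being in the cohort. The value k = 0 is an extreme, because the patient has had part of one infusion and may have had the other in full.

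**The case against.** **The protocol can be read sensibly.** The DLT-free clause speaks of assigned doses, an assigned dose is an amount in mg, and Section 7.4 bars dose modification in Cycle 1. On that reading a truncated infusion already fails the clause. This is probably what was meant, but the protocol does not say it, and the SAP does not carry it over.

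**The group is narrow.** A Grade 2 reaction that settles within an hour need not produce a partial dose. Grade 4 reactions, and Grade 3 reactions outside the exemption, fall under the DLT rules. Doses of 70 mg or less may be given as a 5 to 10 minute bolus (Table JZDA.2.1), which covers four of the seven fixed levels. All of this stands; the point matters mainly from 200 mg upward.

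**There are safeguards.** Cohort decisions are made under the protocol after discussion with investigators, an Escalate may be overridden (7.2.2.1), and adverse events in non-evaluable patients are still reviewed (7.6.1.1). That limits the harm. It does not correct the count entered in the grid or the denominator in the SAP's DLT summary.

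**A stronger reading that a reader might infer.** If *dose* had to mean one thing in both clauses, a patient with a DLT during an unfinished first infusion would not have had one dose, and the DLT would be dropped. A DLT-free replacement would then turn 1/3 Stay into 0/3 Escalate. The documents do not support this. Appendix 1 describes enrolled patients as those who "have received at least one dose of study treatment", and Section 10.2 says that the enrolled/safety population "will include all patients who received any quantity of study treatment", so the protocol treats any exposure as a dose there. The DLT definition in 7.2.2.2 has no amount condition, and SAP 5.2.1 would count the event. Nor does every Grade 3 reaction end treatment, given the 6-hour exception.

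**Conclusion.** The point holds for DLT-free patients. The protocol sets no minimum infused amount, and the SAP rule departs from the protocol by having no dose condition, so a partly dosed patient can be counted as a full DLT-free patient. One such patient can move an Appendix 7 decision up a step.

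The probabilities are bounds, not estimates. At a true 30% DLT rate the chance of escalating after three patients lies between 0.343 (no effect) and 0.490 (the partly infused patient carries no risk); at 50%, between 0.125 and 0.250. Both ranges assume exactly one such patient among the three. How often that would happen cannot be derived from the documents. The loss of a first-infusion DLT is not part of this conclusion.

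**What to change.** 1. In SAP 5.2.1, restore the protocol's dose condition for patients without a DLT, on both routes into the population.
2. In Protocol 7.6.1.1 and SAP 5.2.1, state that a DLT-free patient must have received the full assigned amount of each Cycle 1 infusion, or a minimum share of it. The sponsor should set that share before the first cohort decision. A DLT-free patient below it is non-evaluable and may be replaced.
3. For clarity only, state in both documents that a DLT after any quantity of LY3415244 is evaluable. The existing exception for events attributed to concomitant medication or prior immunotherapy can stay.

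The change takes a few phrases in two documents and alters no dosing or treatment rule. SAP 5.12.1 already needs the actual cumulative dose and reports interruptions, so the added data burden should be small. The downside is an occasional replacement patient, and some delay to a cohort decision, when an infusion is cut short without a DLT.
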